Apart from the main objective, we investigate the effects of the UP on emotion regulation, the role of possible mediators and moderators on outcome, as well as qualitative data on patients' and therapists' experience of psychotherapy. These analyses are specified elsewhere.

Study methods

Design

Please see study protocol (Arnfred et al., 2017)⁷ or www.clinicaltrials.gov (Identifier: NCT02954731).

Randomization

Please see study protocol (Arnfred et al., 2017)⁷.

Sample size

Please see study protocol (Arnfred et al., 2017)⁷.

Correction: In the study protocol we wrote that alpha was set to 5% resulting in a 95% one-sided confidence interval (CI). Following Trial guidelines^{1,8}, the alpha should be 0.025 resulting in a 97.5% one-sided CI. Further, standard deviation (SD) endpoint WHO-5 was reported to be 17.4 WHO-5 points. As reported in Reinholt et al. (2017)⁹ the correct WHO-5 endpoint SD is 20.44. Using these corrected values, then a sample size of 208 patients are required to be 90% sure that the lower limit of a one-sided 97.5% confidence interval (or equivalently a 95% two-sided confidence interval) will be above the non-inferiority limit of -9 WHO-points.

Due to an unexpected, high attrition rate within the first year of inclusion, we decided to adjust sample size calculations by increasing the number of included patients from in total 248 patients to in total 320 patients to get 204 participants completing the treatment as needed for the primary analysis based on our initial sample size calculations. The revised sample size calculation is documented in an amendment to the protocol at www.clinicaltrials.gov (Identifier: NCT02954731).

Timing of outcome assessments

Baseline characteristics will be assessed at the time of inclusion. Outcome measures will be assessed pre-treatment (up to two weeks before start of intervention), post treatment (week 19-21 after allocation), and at six months follow-up (45-47 weeks after allocation). The primary outcome (WHO-5) is further assessed at the beginning of each therapy session (14 sessions).

Timing of final analysis

Primary and secondary outcomes are analyzed post treatment and exploratively repeated at six months follow-up.

Statistical principles

Data presentation

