We will analyze and report primary and secondary outcomes in accordance with CONSORT reporting guidelines for non-inferiority and equivalence trials.² Results from the primary analysis will be reported as between group mean differences with one-sided 97,5% confidence intervals. The focus will be on hypothesis testing rather than point estimation. For secondary analyses, results will be reported as within and between group mean differences with one-sided 97,5% confidence intervals. Effect sizes (Cohens *d*) are calculated for each measure between groups. A one-sided p-value < .025 is considered significant. The focus of secondary analyses will be on point estimation rather than hypothesis testing.

No adjustment for multiplicity will be undertaken. Since outcomes are interrelated, adjustment will be overly conservative.

Adherence and protocol deviations

We will analyze attrition rates (number of patients receiving less than 8 sessions of therapy) in both groups using Chi-square analysis.

The analysis population

In superiority trials, the Intention-to-treat (ITT) analysis is considered the conservative choice to minimize possible type I-errors, that is falsely concluding that the one treatment is superior to another.¹⁰ The ITT population includes all patients randomized and allocated to treatment whether they violated the protocol or dropped out of treatment or not. In superiority trials, the null-hypothesis asserts that there is no difference between the two interventions being compared. The alternative hypothesis being tested is that the two treatments are different by some prespecified value.

A non-inferiority trial, conversely, tries to show that a new treatment is not unacceptably worse than the treatment used for comparison by a prespecified margin.^{11,12} The null hypothesis states that the new treatment is worse than the reference treatment by more than a prespecified non-inferiority margin. In non-inferiority trials, the ITT analysis is conventionally considered a liberal choice because it tends to make the two treatments being compared more similar, possibly falsely inflating type I-errors, that is concluding that the new treatment is non-inferior to the reference treatment. Following CONSORT reporting guidelines, the PP population is, therefore, considered the conservative choice of analysis in non-inferiority trials.²

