The primary analysis will compare the estimated endpoint of the primary outcome (WHO-5) between UP and dCBT conditions post treatment (19 weeks from allocation) adjusted for baseline WHO-5 values, variables predictive for missing data, and stratification variables (i.e. site (Copenhagen, Risskov, Slagelse) and diagnosis (depression, social anxiety disorder, panic disorder/agoraphobia)), fitting treatment (UP or dCBT) as a fixed effects factor.

We will use a one-sided 97.5% CI interval approach to test non-inferiority between conditions. The one-sided 97,5% CI for the between group difference point estimate post treatment will be calculated. Non-inferiority of UP compared to dCBT will be accepted if the lower bound of the 97,5% CI lies within the prespecified non-inferiority margin of – 9 WHO points (see Figure 1). If non-inferiority is accepted, we will use a closed testing procedure to test for superiority of UP over dCBT (i.e. lower bound of the 97,5% CI lies above 0).

The model will be fitted using a multilevel, mixed linear regression model, which allow us to use all 16 WHO-5 outcomes and handle missing data within the model. We will use stratification variables (i.e. site and diagnosis) and baseline outcome variables and treatment as fixed factors. We will apply an unstructured covariance matrix to the random effects in the model. If the model does not converge, we will apply other covariance matrixes (i.e. autoregressive, heterogeneous, compound symmetry, etc.) to the model and choose the covariance matrix with the best fit according to the Akaike Information Criterion. Note: During the blind review of data it turned out that, due to the imputation method used, we were not able to run the analysis applying a unstructured covariance matrix to the random effects in the model as planned Using the Akaike Information Criterion, the autoregressive, 4th order (AR4) covariance matrix,

showed the best fit with the data. Accordingly, the multilevel, mixed linear regression model were run applying the AR4 covariance matrix to the random effects in the model.

Secondary analyses

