For secondary analyses we will use ANCOVA to test for non-inferiority between treatment conditions post treatment. Effect sizes (Cohens *d*) for pre-post differences between and within treatment conditions will be calculated. Following conventions (Cohen, 1988) statistically significant effect sizes ≤ 0.2 will be considered not clinically relevant and for this study a non-inferior difference between conditions.

All analyses will be run allowing for adjustment for stratification variables (i.e. site and diagnosis), and baseline values.

The clinically meaningfulness of results of study will be evaluated calculating numbers and odds ratio for responders and remitted patients using binary logistic regression. 'Responders' are defined as patients receiving a clinically meaningful change in primary outcome, that is ≥ 10 WHO-5 points 'Remission' is defined as patients no longer meeting diagnostic criteria for their primary DSM-5-diagnosis evaluated with the MINI Neuropsychiatric Interview (MINI)²³ 19 weeks after assessment. As an explorative analysis, we will also calculate numbers and odds ratio for patients who no longer met diagnostic criteria for any emotional disorder posttreatment.

Sensitivity analyses

We will run sensitivity analyses for the primary outcome using different definitions of the PP population, depending on how many therapy sessions they attended (i.e. 6, 10 sessions) and using the full ITT-population. Further, we will run a sensitivity analysis without imputed data to assess the potential impact of imputation on the trial findings and assess the impact of missingness by loading the primary analysis using an extreme scenario countering our hypothesis (i.e. imputing the data based on values from the 10% and 90% fractile population). Finally, we will assess the impact of nesting patients in therapy groups by adding therapy group as a random factor. As this analysis might unblind the analyst, this analysis is run after deciphering the blinding.

Additional analyses

Analysis of primary and secondary outcomes will be repeated exploratory at six months follow up.

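### The secondary non-inferiority rule judges the estimated effect size, not a confidence limit, and as written it mislabels results

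*SAP*

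**What the plan says.** The SAP section on secondary analyses states the aim: "For secondary analyses we will use ANCOVA to test for non-inferiority between treatment conditions post treatment". The outcomes concerned are SCL-25, HAM-A6, HAM-D6 and WSAS, as listed under secondary outcomes. The only criterion offered is that "statistically significant effect sizes ≤ 0.2 will be considered not clinically relevant and for this study a non-inferior difference between conditions".

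Three other statements bear on this:

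- Data presentation: "For secondary analyses, results will be reported as within and between group mean differences with one-sided 97,5% confidence intervals".
- Data presentation: "A one-sided p-value < .025 is considered significant". The same paragraph puts the emphasis of the secondary analyses on estimation rather than testing.
- Primary analysis: "Non-inferiority of UP compared to dCBT will be accepted if the lower bound of the 97,5% CI lies within the prespecified non-inferiority margin of" 9 WHO-5 points below zero. This is a confidence-limit rule.

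Nothing connects the 0.2 threshold to the intervals planned under data presentation. No sign convention or standardising SD is given for d.

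**The concern.** A non-inferiority claim should rest on how bad the difference could plausibly be, that is, on the unfavourable confidence limit set against a margin. The primary analysis does this. The secondary rule looks at the point estimate and adds a significance condition which, taken against zero, works backwards: the closer the arms are, the less likely the result is to qualify.

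The sentence can be carried out in at least three ways:

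- **Reading A:** d is significant against zero and |d| ≤ 0.2.
- **Reading B:** as A, but with signed d (positive = UP worse), so any significant benefit of UP also qualifies. With the opposite sign convention, any significant UP deficit would qualify, however large.
- **Reading C:** the observed deficit is at most 0.2, and significance is ignored.

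At stake is whether a non-inferiority label on symptoms or functioning is withheld from equal treatments, or awarded without the error rate the SAP sets. The hypothesis stated in the SAP covers symptom levels as well as well-being, so these labels will be read as answers to it.

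**Working it through.** The SAP states no sample size, power or error rate for the secondary rule, so there is no figure of its own to reproduce.

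**Inputs from the SAP**
- N = 204, from the sample size section: "to get 204 participants completing the treatment as needed for the primary analysis". The 320 to be included serve as an upper case.
- One-sided level 0.025, from data presentation.
- Threshold d = 0.2, from secondary analyses.
- WHO-5 margin of 9 points, and "the correct WHO-5 endpoint SD is 20.44".

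**Assumptions (not given in the SAP)**
- 1:1 allocation.
- Baseline-endpoint correlation r of 0, 0.5 or 0.7.
- d on the endpoint SD, and a normal approximation.
- Imputation and clustering by therapy group ignored. Clustering would widen the standard errors.

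**Standard error of the ANCOVA-adjusted d**

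SE = √[(4/N)(1 − r²)]. For example, at N = 204 and r = 0.7: √(0.0196 × 0.51) = 0.100. The smallest significant |d| is 1.96 × SE.

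| N | r | SE | Smallest significant \|d\| |
|---|---|---|---|
| 204 | 0 | 0.140 | 0.274 |
| 204 | 0.5 | 0.121 | 0.238 |
| 204 | 0.7 | 0.100 | 0.196 |
| 320 | 0 | 0.112 | 0.219 |
| 320 | 0.5 | 0.097 | 0.190 |
| 320 | 0.7 | 0.080 | 0.156 |

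**Reading A.** P(1.96·SE ≤ |d̂| ≤ 0.2):
- N = 204: zero at r = 0 and r = 0.5. At r = 0.7 it is 2[Φ(2.00) − Φ(1.96)] = 0.0045 if true d = 0, and Φ(0) − Φ(−0.04) = 0.016 if true d = 0.2.
- N = 320: zero at r = 0; 1.1% to 4.2% at r = 0.5; 3.8% to 20.7% at r = 0.7 (true d = 0 to 0.2).
- The figures at true d = 0 count both tails; one tail gives half. An observed d of exactly 0 never qualifies. A result in which UP is significantly worse, with d̂ between 0.196 and 0.2 (N = 204, r = 0.7), does.

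**Reading B.** At true d = 0 and N = 204, the favourable tail contributes 2.5%. At r = 0.7 the sliver from 0.196 to 0.2 adds about 0.2%. Equal treatments therefore qualify in 2.5% to 2.7% of trials.

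**Reading C.** P(d̂ ≤ 0.2) = Φ[(0.2 − d)/SE], at N = 204:
- True deficit 0.2: Φ(0) = 50% at any r.
- True deficit 0.3: 23.8%, 20.5% and 15.9% for r = 0, 0.5 and 0.7.
- An observed d of 0.2 has an upper 97.5% limit of 0.2 + 1.96·SE = 0.47, 0.44 and 0.40, yet is labelled non-inferior.

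**A confidence-limit rule at the same threshold.** Requiring d̂ + 1.96·SE < 0.2 holds the false-label rate at a true deficit of 0.2 to 2.5%. Power at true equality is Φ(0.2/SE − 1.96) = 30%, 38% and 52% at N = 204 for r = 0, 0.5 and 0.7. It is low because the trial was sized for a margin of 9/20.44 = 0.44 SD, more than twice 0.2.

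**The case against.** **The secondary analyses are declared to be about estimation, with no multiplicity adjustment.** That is a fair reading of the data presentation section, and the intervals will be reported, so readers can see the uncertainty. But the secondary analyses section still speaks of testing and awards a label. An estimation focus is a reason to drop the label, not to keep a faulty rule for it.

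**The authors may have meant 0.2 as a margin, with significance referring to the non-inferiority test.** This would be a sound confidence-limit rule and may be the intention, but the sentence does not say so. The concessive reading, that an effect of 0.2 or less is unimportant even if significant, still judges the estimate.

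**The figures depend on an SD the SAP does not fix.** This stands. The section speaks of d for pre-post differences. If the adjusted difference were divided by the change-score SD (equal pre and post SDs), SE would be √[(4/N)(1 + r)/2]. The smallest significant d at N = 204 would then be 0.194, 0.238 and 0.253 for r = 0, 0.5 and 0.7, and confidence-limit power 52%, 38% and 34%. The pattern across r reverses, but the conclusion does not change.

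**A confidence-limit rule also withholds the label from equal treatments.** True: in 48% to 70% of trials at N = 204. That is the price of a 0.2 SD margin at this sample size, and it should be stated openly.

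**Conclusion.** The concern holds: the rule is wrong as written. Taken literally (A), it cannot be met by 204 completers at r = 0 or 0.5, and it is met in at most 1.6% of trials at r = 0.7 for true d between 0 and 0.2. With signed d (B), equal treatments qualify in under 3% of trials. With significance set aside (C), the false-label rate at a true deficit of 0.2 is 50%, twenty times the 2.5% the SAP sets. These figures rest on 1:1 allocation, an assumed r of 0 to 0.7 and standardisation on the endpoint SD.

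The matter should be corrected, but its reach is limited. The primary WHO-5 decision is untouched, the intervals will be shown, and only the labels on the four secondary outcomes are affected.

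**What to change.** Replace the sentence with a rule of this kind: UP is called non-inferior on a secondary outcome only if the upper limit of the one-sided 97.5% confidence interval of the adjusted between-group mean difference (UP minus dCBT, higher scores being worse) is below 0.2 times the pooled baseline SD of that scale; significance against zero plays no part. State beside it that power at true equality with 204 completers is about 30% to 52% for an assumed r of 0 to 0.7, taking baseline and endpoint SDs as equal.

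Alternatively, drop the non-inferiority label for secondary outcomes and report adjusted differences with confidence intervals only, which suits the estimation focus the SAP already declares.

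Either way the cost is one or two sentences. The intervals are already planned, and the only added quantity is the pooled baseline SD of each scale, so no interval for d itself is needed. The drawback of the first option is that fewer secondary outcomes can be called non-inferior than if the estimate alone were judged (Reading C).

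### The secondary-outcome rule that d ≤ 0.2 is non-inferior is not tied to a confidence bound, differs from the WHO-5 standard, and is unsound whether read on the estimate or as a margin

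*SAP*

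**What the plan says.** **Primary outcome.** Under Primary analysis, non-inferiority of UP on WHO-5 "will be accepted if the lower bound of the 97,5% CI lies within the prespecified non-inferiority margin" of -9 points. The rule acts on a confidence bound. Under Sample size, the SAP corrects its error rate ("the alpha should be 0.025 resulting in a 97.5% one-sided CI") and its standard deviation ("the correct WHO-5 endpoint SD is 20.44").

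**Secondary outcomes.** These are SCL-25, HAM-A6, HAM-D6 and WSAS. Under Secondary analyses, ANCOVA is given the purpose of testing non-inferiority after treatment. No margin in scale points is set for any of the four. The only criterion is on Cohen's d: statistically significant values up to 0.2 "will be considered not clinically relevant and for this study a non-inferior difference between conditions". The section computes d on pre-post differences. It does not name the standardising SD, the direction of d, or whether 0.2 applies to the estimate or to a bound.

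**Purpose of the secondary analyses.** Under Data presentation: "The focus of secondary analyses will be on point estimation rather than hypothesis testing". The same section plans one-sided 97.5% confidence intervals for these outcomes and sets one-sided p < .025 as significant.

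**The concern.** The same word, non-inferior, is earned in two ways. On WHO-5 it means that a deficit of 9 points or more has been excluded at the 2.5% level. On the symptom and functioning scales it means that d is at most 0.2, with no statement about what has been excluded.

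The introduction hypothesises equal improvement in well-being and symptom levels together, so the verdicts will be read together. A secondary claim of non-inferiority could then be made without the error control that the word carries for WHO-5. If 0.2 is instead taken as a true margin, the claim would usually be out of reach for reasons of sample size alone. Which of these happens is left to whoever applies the sentence.

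**Working it through.** **Inputs.** From the SAP: WHO-5 margin 9 points, endpoint SD 20.44, one-sided alpha 0.025 (1.96), required total 208, secondary criterion d ≤ 0.2. Assumed: 1:1 allocation (104 per arm), no clustering, d expressed in endpoint SDs, and a baseline-to-endpoint correlation r of 0, 0.5 or 0.7. The SAP gives no correlation, so r is a range and not a fact.

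**The plan's own figure.** Total N = 4 × [20.44 × (1.960 + 1.282)/9]² = 216.8, or 218 after rounding up per arm. The stated 208 is not reproduced with SD 20.44; it is with SD 20. At 208 and SD 20.44 the power is 88.8%. This does not affect the point, and 208 is used below only as the size of the trial.

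**Conversion.** 9/20.44 = 0.440 SD. 0.2 × 20.44 = 4.09 points. Ratio 0.440/0.2 = 2.2.

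**Standard error in SD units.** SE = √[(2/104)(1 − r²)]:

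| r | SE | 1.96 × SE |
|---|---|---|
| 0 | 0.139 | 0.272 |
| 0.5 | 0.120 | 0.235 |
| 0.7 | 0.099 | 0.194 |

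**Reading A: 0.2 limits the estimate.**
- The confidence limit for an estimated deficit of exactly 0.2 is 0.2 + 1.96 × SE = 0.47, 0.44 and 0.39 SD.
- The chance of passing at a true deficit of 0.2 SD is 50% for every r, since the estimate falls on either side equally often. A rule based on a confidence bound passes 2.5% of the time at its own margin.
- The chance of passing at a true deficit of 0.3 SD is Φ((0.2 − 0.3)/SE) = 24%, 20% and 16%.

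**Reading B: 0.2 is a margin for the confidence bound.**
- With truly equal arms the chance of passing is Φ(0.2/SE − 1.96) = 30%, 38% and 52%. With the 204 completers that the SAP aims for, the figures are the same after rounding.
- With all 320 patients, complete data and r = 0, it is 43%.
- A 90% chance would need 1052, 790 or 536 patients in total.

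**The WHO-5 rule for comparison.** It passes when the observed deficit is at most 0.440 − 1.96 × SE = 0.17, 0.20 and 0.25 SD.

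**The case against.** The strongest case against is that nothing here is contradictory. The 0.2 sentence stands under Secondary analyses, WHO-5 has its own margin, and different outcomes may have different margins. That stands.

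A reader might infer something stronger: that the same standardised deficit is declared non-inferior on WHO-5 and clinically relevant on the symptom scales. The SAP does not support this, for three reasons.
- It says that d up to 0.2 is not relevant. It never says that a larger d is.
- The -9 limit acts on a confidence bound, while 0.2 most naturally reads as a limit on the estimate. On observed deficits the two rules nearly coincide: 0.17 to 0.25 SD against 0.2.
- The 0.44 SD figure uses the endpoint SD, whereas d is computed on pre-post differences with an unstated SD. The two may not be on one scale.

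It can also be said that, on Reading A, the confidence limit of 0.39 to 0.47 SD is close to the WHO-5 margin, so the secondary rule is no laxer in effect. The numbers are right, but the agreement is a by-product of sample size and correlation. The SAP nowhere adopts 0.44 SD as a margin for the symptom scales. The verdict would be announced against 0.2 while the data left about twice that open.

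Finally, the word focus under Data presentation is an emphasis and not a ban on testing, since a significance level is set just before it. That also stands. The tension between the two sections is real but mild.

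**Conclusion.** The point holds in this form: the secondary non-inferiority verdict is set by a different standard from the primary one and is unsound on both available readings. On the estimate, it passes half the time at a true deficit of 0.2 SD and leaves up to 0.39 to 0.47 SD unexcluded. As a confidence margin, it passes truly equal arms only 30 to 52% of the time. These figures rest on 104 per arm, an assumed r of 0 to 0.7, no clustering, and d in endpoint SDs; they would shift if d is standardised by the SD of change.

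The sentence also requires statistical significance. At this sample size an unadjusted d must be about 0.27 to be significant, so read literally the rule would almost never apply. The point does not depend on that.

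None of this calls the 9-point margin or its decision rule into question. It matters for what the trial may claim on symptoms and functioning, not for the primary conclusion.

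**What to change.** In the SAP's Secondary analyses section:
- Delete the clause in the effect-size sentence that turns not clinically relevant into a non-inferiority verdict for this study.
- Delete the statement that the purpose of the ANCOVA is to test non-inferiority.
- State that SCL-25, HAM-A6, HAM-D6 and WSAS are reported as adjusted between-group differences and Cohen's d with confidence intervals, without a non-inferiority verdict. This matches the stated focus under Data presentation.

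Leave the 9-point WHO-5 margin and its rule unchanged, and add no 0.2 SD check to WHO-5.

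The cost is a change of wording and the loss of a formal non-inferiority claim on the secondary outcomes. No data, model or sample size changes.

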Given the potential biases in both PP and ITT analysis, the European Medicines Agency (EMA) in the paper *'Points to consider when switching between superiority and non-inferiority'* states that inference of non-inferiority should rely on both PP and ITT-analyses.⁸ Other authors (i.e. Sanchez & Chen, 2006¹³) argue that showing non-inferiority in both sets of analysis does not guarantee a valid conclusion as the conservatism or non-conservatism of the PP population depends on several factors, including the quality of the study, type of protocol violations and missingness. Sanchez & Chen (2006)¹³ recommend minimizing the impact of protocol violations and missingness in the statistical analysis by using a hybrid ITT/PP analysis which excludes non-compliant patients as in the PP population and properly addresses the impact of non-trivial missing data in an ITT analysis. We will use this hybrid model for analysis of primary and secondary outcomes.

For this analysis plan, the PP population is defined as patients completing the therapy (i.e. receiving eight therapy sessions or more). The ITT population is defined as all patients randomized and allocated to treatment.

Trial population

Eligibility

Please see study protocol (Arnfred et al., 2017)⁷ or www.clinicaltrials.gov (Identifier: NCT02954731).

Recruitment

Please see study protocol (Arnfred et al., 2017)⁷ or www.clinicaltrials.gov (Identifier: NCT02954731).

Participant flow

The number of patients screened, randomized, completed treatment, and completed follow-up outcomes, will be summarized in a CONSORT flow diagram.³

Baseline characteristics

The following demographic and illness burden variables will be summarized by treatment condition in Table 1: age, sex, immigrant status, marital status, level of employment, level of education, children living at home, comorbidity, previous psychological treatment, current medication, age of onset, previous episodes with primary diagnosis, previous hospitalization, and personality traits (Standardized Assessment of Personality Abbreviated Scale (SAPAS)).¹⁴

Analysis

Primary outcome

The primary outcome is self-reported subjective well-being measured with the WHO-5 assessed post treatment (19 weeks after allocation; single score continuous outcome).

Secondary outcomes

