Adverse events will be listed by group and type of event: (a) Minor adverse events will be reported as number of patients encountering any of these: increasing current medication more than one standard dose step; using according-to-need medication for more than two weeks; increasing current medication to entail more than four types of psychotropic medications; new prescription of supplementary medication (accepted at inclusion); changing previously prescribed antidepressant to another type. (b) Major adverse events will be reported as number of events: New prescription of medication (not accepted at inclusion); contacting psychiatric emergency due to self-injury; suicide attempt without hospitalization; drop-out of therapy due to experienced lack of effect or deterioration. (c) Critical adverse events will be reported as number of events: psychiatric hospitalization due to deterioration or suicide attempt; somatic hospitalization due to self-injury or suicide attempt; referral to electroshock treatment; suicide.

Model checking and validation

We will check the robustness of models by examining residuals.

Handling of missing data and blinding

Data entry is performed by the data manager and research assistants according to the main study protocol. We will undertake a blinded analysis of missing data and outliers to evaluate how to deal with missing data and outliers, and to explore possible predictors of missing data which should be controlled for in the primary and secondary analyses. The analysis of the primary and secondary outcomes will be conducted with the treatment allocation blinded. In the data extraction for the primary analysis, the intervention type is concealed. The intervention and control arm will randomly be coded as '1' and '2'. Deciphering will not be done before all analyses at post-treatment have been performed, and conclusions for the primary outcome has been formulated.

For this analysis plan, we define missing data as those patients with the absence of data at follow-up for one or more outcomes. Data are assumed to be missing at random.

In the primary analysis, the mixed linear regression model handles missing data by full information maximum likelihood, except for the baseline value of WHO-5. Missing baseline WHO-5 values will be handled by multiple imputation with chained equations (m=100) using stratification variables, post-baseline values and variables predicting missing baseline WHO-5 as predictors in the imputation model.

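### By the SAP's general rule, response and remission would be analysed only in patients with 8 or more sessions, and no all-allocated analysis of them is planned

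*SAP*

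**What the plan says.** Four parts of the SAP bear on this.

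- **Secondary analyses.** "The clinically meaningfulness of results of study will be evaluated calculating numbers and odds ratio for responders and remitted patients using binary logistic regression". Response is a WHO-5 change of at least 10 points. Remission is no longer meeting criteria for the primary diagnosis on the MINI. A further exploratory endpoint is no longer meeting criteria for any emotional disorder. No analysis population is given for any of the three.
- **The analysis population.** The SAP adopts a hybrid ITT/PP approach that "excludes non-compliant patients as in the PP population" and then says: "We will use this hybrid model for analysis of primary and secondary outcomes". Per protocol means at least eight sessions. ITT is defined separately: "The ITT population is defined as all patients randomized and allocated to treatment".
- **Sensitivity analyses.** "We will run sensitivity analyses for the primary outcome using different definitions of the PP population", with cut-offs of 6 and 10 sessions and with the full ITT population. The extreme-value imputation scenario is likewise tied to the primary analysis.
- **Adverse events.** Major adverse events include "drop-out of therapy due to experienced lack of effect or deterioration". No session limit is attached.

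**The concern.** Response and remission are the endpoints from which the SAP will say whether patients benefited in a clinically meaningful way. A reader will take a response rate as the chance of benefit for someone allocated to that treatment. If the denominator holds only patients who reached eight sessions, membership is decided after randomisation and partly by how treatment was going. A patient who stops at session 4 because therapy is not working would be a major adverse event in the safety listing, but neither a non-responder nor a non-remitter in the efficacy table.

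The SAP's reason for preferring a per-protocol set is specific to non-inferiority: ITT tends to make the arms look alike and so makes a false non-inferiority claim easier. These odds ratios have no margin and test no non-inferiority hypothesis. They describe benefit and the difference between arms. For a superiority question the same section of the SAP calls ITT the conservative choice.

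**Working it through.** **Step 1: which patients are in the analysis.** The chain is: hybrid set for primary and secondary outcomes; the hybrid set drops non-compliant patients as the PP set does; PP means eight or more sessions; response and remission stand under Secondary analyses with no other population named. The full-ITT rerun is limited to the primary outcome. Multiple imputation (Handling of missing data and blinding) fills missing values, but nothing says that it returns patients excluded for too few sessions. Followed as written, no planned analysis puts those patients into the response or remission denominators.

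**Step 2: how many.** SAP, Sample size: 320 included, 204 expected to complete treatment.

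- Retained: 204/320 = 63.75%
- Excluded: 320 − 204 = 116; 116/320 = 36.25%

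**Step 3: effect on the rate.** The SAP gives no response rate, so this is an illustration. Let r be response in completers, a the excluded share, and f the fraction of excluded patients who fail, the rest responding at r. The all-allocated rate is

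p = (1 − a)r + a(1 − f)r = r(1 − fa).

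With r = 60% (assumption) and a = 36.25%:

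- f = 1: 0.60 × 0.6375 = 38%
- f = 0.5: 0.60 × (1 − 0.18125) = 49%
- f = 0: 60%, the completer figure

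**Step 4: effect on the odds ratio.** Assumptions: 160 per arm, r = 60% in both arms, attrition 41% in UP and 31% in dCBT. Completers number 94.4 and 110.4, and the completer odds ratio is 1.00.

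| Excluded who fail | UP | dCBT | All-allocated OR |
|---|---|---|---|
| all (worst case) | 0.60 × 0.590 = 35.4% | 0.60 × 0.690 = 41.4% | (0.354/0.646)/(0.414/0.586) = 0.78 |
| half | 0.60 × 0.795 = 47.7% | 0.60 × 0.845 = 50.7% | (0.477/0.523)/(0.507/0.493) = 0.89 |
| a quarter | 0.60 × 0.8975 = 53.9% | 0.60 × 0.9225 = 55.4% | 0.94 |

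If the attrition figures are swapped between arms, the ratios invert: 1/0.776 = 1.29 in the worst case. If attrition is 36.25% in both arms, early leavers fare alike and completers respond equally, the odds ratio stays at 1.00 and only the rates fall.

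A different set of assumptions gives a similar picture. With 50% response in completers and attrition of 41.25% and 31.25%, the odds ratio is 0.79 if all excluded patients fail and 0.88 if they respond at 20%.

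**The case against.** Several stronger readings are tempting, and the SAP does not support them.

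- *The SAP states that these endpoints are completer-only.* It does not. The paragraph is silent, and neither endpoint is in the SAP's list of secondary outcomes. The eight-session set is inferred from the general rule and the heading. If the rule does not reach these endpoints, their population is undefined, which also needs fixing.
- *Every patient who left because therapy failed is lost.* With 14 sessions, someone who leaves for lack of effect after reaching eight stays in the PP set. The adverse-event category and the excluded group overlap but are not the same, and patients also leave early for other reasons.
- *The plan hides failures and favours UP.* Attrition below eight sessions is compared between arms by chi-square, and these drop-outs are listed by group. The SAP gives no attrition by arm, so the direction of any bias is unknown.
- *38% and 0.78 are the expected corrected figures.* They count every excluded patient as a failure and are a worst case.

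The best defence of the plan is that the non-inferiority decision rests on continuous WHO-5 and is untouched, that continuous WHO-5 does get a full-ITT analysis, and that describing clinical meaningfulness in the set that yields the primary result is coherent. This is a fair reason to keep the completer version. It does not supply an all-allocated estimate of response or remission. Remission has no counterpart in the primary outcome's ITT rerun, and reporting attrition elsewhere does not correct the rates or the odds ratios.

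**Conclusion.** The point holds as a gap in the analysis of response and remission, by the most natural reading of the SAP. On its own planning figures, 116 of 320 patients (36%) would be outside both denominators, with no analysis that restores them. The reported rates would overstate benefit per allocated patient unless early leavers do as well as completers. The odds ratio may be off in either direction if early drop-out differs by arm. It need not move if drop-out and early leavers' outcomes are equal.

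The 36% rests on the SAP's figures. The response rates, the arm-specific attrition and the share of early leavers who fail are assumptions. Under those used here, an odds ratio of 1.00 moves to between 0.78 and 0.94 with higher UP attrition, and to the reciprocals with higher dCBT attrition. The primary test is not affected. The statement of clinical benefit is, so the sponsor should act.

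**What to change.** In Secondary analyses, state the population for response, remission and the any-emotional-disorder endpoint. Add an analysis of all three in all patients randomised and allocated, as follows:

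- use the observed week 19–21 WHO-5 and MINI values regardless of sessions attended;
- count a patient with no value who is logged as dropping out for lack of effect or deterioration as a non-responder and as not remitted;
- multiply impute the remaining missing values.

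Report this beside the version restricted to eight or more sessions, and give the difference in proportions with its 95% CI next to each odds ratio. If the allocation code has already been broken, label the analysis as added afterwards.

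**Cost.** The change needs SAP wording and reruns of the logistic models. The planned imputation must also be extended to patients with fewer than eight sessions (about 116 on the planning figures), including binary MINI status. Drop-out for lack of effect or deterioration is already to be recorded for the adverse-event listing. The reported rates will probably be lower.
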